10.3 Subject Information and Informed Consent

The study will be conducted in accordance with applicable subject privacy requirements. The proposed ICF, which must be in compliance with applicable regulations, must be reviewed and approved by the EC and Harbour BioMed prior to initiation of the study.

The Investigator will be responsible for obtaining written informed consent from potential subjects prior to any study-specific screening and enrollment. A copy of the signed ICF will be provided to the subject. The original will be retained by the Investigator.

10.4 Laboratory Accreditation

Any laboratory facility intended to be used for analysis of clinical laboratory samples required by this protocol must provide evidence of adequate licensure or accreditation according to the prevailing regulations. Reference values and/or normal ranges for the test results must be provided to Harbour BioMed. Sponsor must be notified promptly in writing of any changes occurring in reference values during the course of the study.

10.5 Confidentiality

10.5.1 Data Confidentiality

By signing this protocol, the Investigator affirms to Harbour BioMed that information provided to the Investigator by Harbour BioMed will be maintained in confidence and such information will be disclosed to the EC, or similar organizations or expert committee; affiliated institution and employees only after confirming the confidentiality of such board or committee, affiliated institution and employees. Data generated by this study will be considered confidential except those included in a publication.

10.5.2 Confidentiality of Subject / Patient Records

By signing this protocol, the Investigator agrees that Harbour BioMed (or representative), EC, or Regulatory Agency representatives may review and/or copy study documents to verify worksheet/case report form data. By signing the consent form, the subject/patient agrees to this process. If study documents will be photocopied during the process of verifying worksheet/case report form information, the subject/patient will be identified by unique code only; full names/initials will be masked before sending the document to Harbour BioMed. In addition, the Investigator agrees to treat all subject data used and disclosed in connection with this study in accordance with all applicable laws (such as the Health Insurance Portability and Accountability Act), rules and regulations.

10.6 Quality Control and Assurance

Harbour BioMed will be responsible for implementing and maintaining quality control and quality assurance systems with written SOPs to ensure that the study will be conducted and data will be generated, documented, and reported in compliance with the protocol, accepted standards of GCP, and all applicable local laws relating to the conduct of the clinical study.

10.7 Data Management

Data management procedures and information for this protocol will be provided by Harbour BioMed or its designee.

10.8 Study Monitoring

In accordance with applicable regulations, GCP, and Harbour BioMed procedures, clinical research associates (CRAs) will contact the site prior to subject enrollment to review the protocol and data collection procedures with site staff. In addition, the CRA will periodically contact the site, including conducting on-site visits. The extent, nature, and frequency of on-site visits will be based on the study objective and/or endpoints, the purpose of the study, study design complexity, and enrollment rate.

During these procedures, the CRA will:

- Check the progress of the study;
- Review study data collected;
- Conduct source document verification;
- Identify and address any issues.

The work above is to verify that:

- The data are authentic, accurate, and complete;
- Safety and rights of subjects are being protected.
- Study is conducted in accordance with the currently approved protocol (and any amendments), GCP, and all applicable regulatory requirements.

The Investigator agrees to allow the CRA direct access to all relevant documents and to allocate his/her time to the CRA to discuss findings and any relevant issues.

Upon completion of the study, the CRA will conduct the following activities in conjunction with the Investigator or site staff, as appropriate:

- Return of all study data to Harbour BioMed;
- Data queries;
- Accountability, reconciliation, and arrangements for unused study drugs;
- Review of site study records for completeness.

After the final review of the study files, the files should be secured for the appropriate time period. The Investigator will also permit inspection of the study files by Quality Assurance auditors from Harbour BioMed, and authorized representatives of the NMPA or other applicable regulatory agencies.

10.9 Data Retention

Documents that individually and collectively being evaluable for the conduct of the study and the quality of the data must be maintained for review by quality assurance auditors from Harbour BioMed and by all applicable regulatory authorities. The period of time for which these documents must be maintained is determined by applicable regulations. Harbour BioMed or its designee will inform the Investigator when these documents may be destroyed. Harbour BioMed or its designee must be notified in writing prior to the intended date of disposal of any study record related to this protocol for making alternate storage arrangements.

10.10 Financial Disclosure

The Principal Investigator or sub-Investigators will need to complete a financial disclosure form prior to study initiation, at any time during the study execution if new information needs to be disclosed.

12 APPENDICES

12.1 APPENDIX 1: EXAMINATION PROCEDURE, TESTS, EQUIPMENTS AND TECHNIQUES

Visual Acuity Procedures (ETDRS Chart)

LogMAR visual acuity (VA) must be assessed using an Early Treatment Diabetic Retinopathy Study (ETDRS) chart. The procedure used will be consistent with the recommendations provided for using the ETDRS eye chart. VA should be evaluated at the beginning of each visit in the study (ie, prior to slit-lamp examination). VA testing should be done with most recent correction.

Equipment

The VA form used is the ETDRS Charts. If a small wall chart (18 "x 18", such as blindness prevention) is used, the measuring distance for subjects should be as accurate as 10 feet (or as per manufacturer instructions). In all cases, all the study sites can only use the same target form and should first test the right eye in order to standardize the test conditions during the study. For reflection-type wall charts, they should be placed right ahead, good lighting should be provided.

Measurement Technique

The chart should be at a comfortable viewing angle. The right eye should be tested first. The subject should attempt to read each number target, line-by-line, left to right, beginning with line 1 at the top of the chart. The subject should be told that the chart has numbers only, no letters. If the subject reads a letter, he or she should be reminded that the chart contains no letters, and the examiner should then request a number in lieu of the letter. The subject should be asked to read slowly, so as to achieve the best identification of each number. He/she is not to proceed to the next number until he/she has given a definite response.

If the subject changes a response (e.g., 'that was a "9" not an "3"') before he has read aloud the next number, then the change must be accepted. If the subject changes a response having read the next number, then the change is not to be accepted. The examiner should never point to the chart or to specific numbers on the chart during the test.

A maximum effort should be made to identify each number on the chart. When the subject says he or she cannot read a number, he or she should be encouraged to guess. If the subject identifies a number as 1 of 2 numbers, he or she should be asked to choose 1 number and, if necessary, to guess. When it becomes evident that no further meaningful readings can be made, despite encouragement to read or guess, the examiner should stop the test for that eye. However, all letters on the last line should be attempted as number difficulties vary and the last may be the only one read correctly. The targets missed or read incorrectly should be noted.

LogMAR Visual Acuity Calculations

The last line in which a number is read correctly will be taken as the base logMAR reading. To this value will be added the number "N x 0.02" where 'N' represents the total number of number targets missed up to and included in the last line read. This total sum represents the logMAR VA for that eye.

For Example: Subject correctly reads 4 of 5 numbers on the 0.2 line, and 2 of 5 numbers on the 0.1 line.

Base logMAR	= 0.1
N (total number of targets incorrect on line 0.2 as well as 0.1)	= 4
$N \times T$ (T=0.02)	= 0.08
Base logMAR + (N x T)	= 0.1 + 0.08
logMAR VA	= 0.18

Repeat the procedure for the left eye.

In order to provide standardized and well-controlled assessments of VA during the study, all VA assessments at a single site must be consistently done using the same lighting conditions and same correction if possible during the entire study. If the same correction cannot be used (ie, a subject forgets his glasses), the reason for the change in correction should be documented.

Slit Lamp Biomicroscopy Procedures

Slit lamp biomicroscopic observations will be graded as Normal or Abnormal. Abnormal findings will be categorized as clinically significant (findings that may interfere with study parameters or otherwise confound the data as determined by the investigator) or not clinically significant (NCS). The following will be examined:

- Cornea
- Conjunctiva
- Anterior Chamber
- Iris
- Lens
- Eyelid

External magnification and biomicroscopy will be performed using a slit-lamp. Magnification will be consistent with standard clinical practice. The subject will be seated.

Fundus Color Photography

The fundus color camera will be used to take photos of the patients' fundus, and the photos will be kept. Pupil dilation is not a must, but the photos must be clear and include optic discs and macula lutea. The Investigator will examine the vitreous body, retina, macula lutea, choroid, and optic nerves.

Observations will be graded as Normal or Abnormal. Abnormal findings that are clinically significant (as determined by the Investigator that may interfere with study parameters or otherwise confound the data) and those that are not clinically significant will be described. An indirect ophthalmoscope or preset lens examination should be performed if retinal disease is detected or optic discs and macula lutea can't be photographed simultaneously.

- Vitreous: Examination should emphasize the visual axis.
- Retina, Macula, Choroid: Include an observation of the retina and its blood vessels. Eyes should be excluded from the study if active inflammation is present.
- Optic Nerve: Significant damage or cupping to the optic nerve should be noted.

It is recommended that tropicamide 1% ophthalmic solution be used to dilate subjects. The use of cyclopentolate 1% ophthalmic solution is recommended as secondary dilating medication, should the need arise.

Intraocular Pressure

Intraocular pressure (IOP) will be measured in each eye by non-contact tonometry by the examiner and the results will be recorded in mmHg. The measurement of intraocular pressure will be repeated three times to calculate the mean value. If the variation is large, the measurement will be repeated as appropriate to calculate the mean value.

Ora proprietary scales – Not for distribution without permission

Ora Calibra® Ocular Discomfort Scale for Dry Eye

Ocular discomfort scores will be subjectively graded by the subjects according to the following scale, rating each eye separately.

0	No discomfort
1	Intermittent awareness
2	Constant awareness
3	Intermittent discomfort
4	Constant discomfort

Ora Calibra® Eye Discomfort and 4-Symptom Dry Eye Questionnaire

At each day during the at-home dosing period, subjects will grade the severity of their dry eye syndrome symptoms in their diary in the morning and in the evening, before instilling the study drug.

Subjects will rate the severity of each of the following symptoms, with regards to how both their eyes feel, in general – overall ocular discomfort, burning, dryness, grittiness and stinging according to the following 6-point (0 to 5) scale where 0 = none and 5 =worst.

0	1	2	3	4	5
(None)					(Most)

Visual Analog Scale (VAS)

The subject will be asked to rate each ocular symptom due to ocular dryness by placing a vertical mark on the horizontal line to indicate the level of discomfort. 0% corresponds to “no discomfort” and 100% corresponds to “maximal discomfort.”

Burning/Stinging	0%	100%
Pruritus	0%	100%
Foreign body sensation	0%	100%
Blurred vision	0%	100%
Eye dryness	0%	100%
Photophobia	0%	100%
Pain	0%	100%

Ocular Surface and Disease Index (OSDI)[®] for Dry Eye

Ocular Surface Disease Index[®] (OSDI[®])²

Ask the patients the following 12 questions, and circle the number that best represents the answer of each question. Then fill in the boxes A, B, C, D and E according to the instructions beside each.

Have you experienced any of the following during the last week?	All of the time	Most of the time	Half of the time	Some of the time	None of the time
1. Eyes that are sensitive to light?	4	3	2	1	0
2. Eyes that feel gritty?	4	3	2	1	0
3. Painful or sore eyes?	4	3	2	1	0
4. Blurred vision?	4	3	2	1	0
5. Poor vision?	4	3	2	1	0

Subtotal score for answers 1 to 5

Have problems with your eyes limited you in performing any of the following during the last week?	All of the time	Most of the time	Half of the time	Some of the time	None of the time	N/A
6. Reading?	4	3	2	1	0	N/A
7. Driving at night?	4	3	2	1	0	N/A
8. Working with a computer or bank machine (ATM)?	4	3	2	1	0	N/A
9. Watching TV?	4	3	2	1	0	N/A

Subtotal score of answers 6 to 9

Have your eyes felt uncomfortable in any of the following situations during the last week?	All of the time	Most of the time	Half of the time	Some of the time	None of the time	N/A
10. Windy conditions?	4	3	2	1	0	N/A
11. Places or areas with low humidity (very dry)?	4	3	2	1	0	N/A
12. Areas that are air conditioned?	4	3	2	1	0	N/A

Subtotal score of answers 10 to 12

Add the subtotals A, B and C to obtain D (D = sum of scores for all questions answered)

(D)

Total number of questions answered (do not include questions answered N/A)

(E)

[figure not shown]
Please turn over the questionnaire to calculate the patient's final OSDI score.

Evaluating the OSDI[®] score¹

The OSDI[®] is assessed on a scale of 0 to 100, with higher scores representing greater disability. The index demonstrates sensitivity and specificity in distinguishing between normal subjects and patients with dry eye disease. The OSDI[®] is a valid and reliable instrument for measuring dry eye disease (normal, mild to moderate, and severe) and effect on vision-related function.

Assessing Your Patient's Dry Eye Disease^{1,2}

Use your answers D and E from side 1 to compare the sum of scores for all questions answered (D) and the number of questions answered (E) with the chart below.* Find where your patient's score would fall. Match the corresponding shade of red to the key below to determine whether your patient's score indicates normal, mild, moderate, or severe dry eye disease.

1. Data on file, Allergan, Inc.

Ora Calibra® Conjunctival Redness Scale for Dry Eye

None	0 = Normal, no vascular dilation
Trace	1 = Trace ciliary or conjunctival vasodilation
Mild	2 = Broad ciliary vasodilation;
Moderate	3 = Broad ciliary and slight, horizontal conjunctival vasodilation
Severe	4 = Broad ciliary and prominent, horizontal conjunctival vasodilation
Half (0.5) unit increments are allowed.	

Tear Film Break-Up Time (TFBUT)

The examiner will instill 5 µL of 2% preservative-free sodium fluorescein solution into the inferior conjunctival cul-de-sac of each eye or use the sodium fluorescein test strips for staining (moisturized in saline). To thoroughly mix the fluorescein with the tear film, the subject will be instructed to blink several times. In order to achieve maximum fluorescence, the examiner should wait approximately 30 seconds after instillation before evaluating TFBUT.

With the aid of a slit-lamp, the examiner will monitor the integrity of the tear film, noting the time it takes to form micelles from the time that the eye is opened. TFBUT will be measured in seconds using a stopwatch for the right eye followed by the left eye. A Wratten #12 yellow filter will be used to enhance the ability to grade TFBUT.

For each eye, 2 measurements will be taken and averaged unless the 2 measurements are > 2 seconds apart and are each < 10 seconds, in which case, a third measurement would be taken and the 2 closest of the 3 would be averaged.

Fluorescein Staining

[figure not shown]
The examiner drips 5µL of 2% preservative-free sodium fluorescein solution or use the sodium fluorescein test strip for staining (moisturized in saline) to the subconjunctival posterior fornix of each eye. In order to maximize fluorescent staining, the examiner should wait for about 3-5 minutes after dripping the dyes, and then assess fluorescein staining. Use the Wratten #12 yellow optical filter to enhance rating of fluorescein staining, and the Ora Calibra® corneal and conjunctival fluorescein staining scale to rate staining (the NEI scale may be used for re-assessment after assessment with this scale).

Ora Calibra® Corneal and Conjunctival Staining Scale for Grading of Fluorescein Staining

The following scale will be used to grade staining of the ocular surface (areas A, B, C, D, and E). Half (0.5) grade increments may be used.

None	0 = No staining
Slight	1 = Occasional
Mild	2 = Countable
Moderate	3 = Uncountable, but unfused
Severe	4 = Fusion

Staining areas:

Staining Areas	Ocular Structure	Position
A – Inferior	Cornea	4-8 o'clock, extending 2 mm onto the conjunctiva
	Limbus/conjunctiva	4-8 o'clock, extending 2 mm towards the center
B – Superior	Cornea	8-4 o'clock, extending 3 mm onto the conjunctiva
	Limbus/Conjunctiva	8-10 o'clock and 2-4 o'clock, extending 1 mm onto the conjunctiva; 10-2 o'clock, extending 2 mm onto the conjunctiva
C - Central	Cornea	Central cornea
D – Temporal	Conjunctiva	Triangular wedge of temporal conjunctiva
E = Nasal	Conjunctiva	Triangular wedge of nasal conjunctiva

Unanesthetized Schirmer's Test

Schirmer Tear Test will be performed according to the following procedure:

- Using a sterile Schirmer test strip, a bend in the strip will be made in line with the notch in the strip
- The subject will be instructed to gaze up and in
- The Schirmer test strip will be placed in the lower temporal lid margin of each eye such that the strip fits tightly. Subjects will be instructed to close their eyes
- After 5 minutes have elapsed, the Schirmer strip will be removed. The length of the moistened area will be recorded (mm) for each eye

7. Safety Analysis.....	17
7.1 Adverse Event	17
7.2 Other Safety Endpoints	18

List of Abbreviations

AE	Adverse Event
ANCOVA	Analysis of Covariance
ATC	Anatomical Therapeutic Chemical Classification
BCVA	Best Corrected Visual Acuity
CAE	Controlled Adverse Environment
CI	Confidence Interval
CRF	Case Report Form
CRO	Contract Research Organization
CS	Clinically Significant
CSR	Clinical Study Report
eCRF	Electronic Case Report Form
ETDRS	Early Treatment of Diabetic Retinopathy Study
ICH	International Conference on Harmonisation
IOP	Intraocular Pressure
IP	Investigational Product
ITT	Intent-to-Treat
LOCF	Last Observation Carried Forward
logMAR	Logarithm of the Minimum Angle of Resolution
MedDRA	Medical Dictionary for Regulatory Activities
NCS	Not clinically significant
OSDI	Ocular Surface Disease Index
PP	Per Protocol
PT	Preferred Term
SAE	Serious Adverse Event
SAP	Statistical Analysis Plan
SD	Standard Deviation
SDC	Statistics and Data Corporation, Incorporated
SOC	System Organ Class
SOP	Standard Operating Procedure
TEAE	Treatment-Emergent Adverse Event
TE-SAE	Treatment-Emergent Serious Adverse Event
TFBUT	Tear Film Break-Up Time
VA	Visual Acuity
VAS	Visual Analogue Scale
WHO DDE	World Health Organization Drug Dictionary Enhanced

1. Introduction

The purpose of this statistical analysis plan (SAP) is to describe the planned analyses and reporting for protocol HBM9036. Samples reporting tables, figures, and listing (TFL) can be found in a separate document (TFL shells, to be named).

1.1 Study Objectives and Endpoints

The objectives of this study are to compare the safety and efficacy of 0.25% HBM9036 Ophthalmic Solutions to placebo for the treatment of the signs and symptoms of moderate to severe dry eye.

The primary objective is to evaluate the efficacy of 8-week continuous treatment with HBM9036 ophthalmic solution (BID) in Chinese patients with moderate and severe dry eye and to provide information for the Phase III trial decision.

The primary efficacy endpoint is:

- The change from baseline in change from pre- to post-CAE[®] inferior corneal staining score (ICSS) of the study eye evaluated at Visit 6 (Day 57, Week 8) according to Ora Calibra[®] Corneal and Conjunctival Fluorescein Staining Scale (Referred to as $\Delta\Delta\text{ICSS}$ at Day 57)

Secondary efficacy endpoints are:

- $\Delta\Delta\text{ICSS}$ at Visit 5 (Day 29)
- The change from baseline in pre-CAE[®] ocular discomfort of the study eye evaluated at Visit 6 according to Ora Calibra[®] Ocular Discomfort Scale
- The change from baseline in pre-CAE[®] ocular discomfort of the study eye evaluated at Visit 5 according to Ora Calibra[®] Ocular Discomfort Scale
- The change from baseline in pre-CAE[®] symptom score evaluated at Visit 6 according to Ora Calibra[®] Ocular Discomfort and 4-Symptom Questionnaire
- The change from baseline in pre-CAE[®] symptom score evaluated at Visit 5 according to Ora Calibra[®] Ocular Discomfort and 4-Symptom Questionnaire
- The change from baseline in post-CAE[®] TFBUT[®] of the study eye evaluated at Visit 6
- The change from baseline in post-CAE[®] conjunctival redness score of the study eye evaluated at Visit 6 according to Ora Calibra[®] Conjunctival Redness Scale

- The change from baseline in Schirmer's test results at Visit 6
- The changes from baseline in OSDI[®] scores at Visit 6
- The change from baseline in pre-CAE[®] burning sensation score evaluated at Visit 6 according to Visual Analogue Scale (VAS)
- The change from baseline in average weekly burning sensation score in subject diary at Week 8

1.2 Study Design

This is a multi-center, randomized, double blind, placebo control study. One hundred (100) study subjects are randomly assigned to either HBM9036 or placebo group in a 1:1 ratio. Randomized study subjects receive the first dose of study drug on the randomization day (referred to Day 1). Study subjects receive 8 weeks of study drug treatments. Study subjects return to the office on Day 8 (Visit 3), Day 15 (Visit 4), Day 29 (Visit 5), and Day 57 (Visit 6) for efficacy and safety assessments. The End of Study (EoS) is a telephone safety follow-up 7 days after the last dose of study drug. More details can be found in the study protocol.

1.3 Statistical Hypotheses for Trial Objectives

The statistical hypothesis of this study is:

H₀: There is no difference between HBM9036 ophthalmic solution (0.25%) and placebo in the change from baseline of the change from pre- to post-CAE[®] ICSS of the study eye at Visit 6 (Day 57, Week 8), according to Ora Calibra[®] Corneal and Conjunctival Fluorescein Staining Scale.

H₁: The change from baseline of the change from pre- to post-CAE[®] ICSS of the study eye at Visit 6 (Day 57, Week 8) using the Ora Calibra[®] scale is different with HBM9036 ophthalmic solution (0.25%) from with placebo.

1.4 Sample Size Justification

This study plans to enroll 50 subjects in each treatment group so a total of 100 subjects will be randomized. Assuming a 20% drop out rate, 40 subjects per group are expected to complete the study.

The treatment effect is of little clinical relevance if the difference between HBM9036 and placebo in the primary endpoint is greater than -0.1. In contrast, if the difference is -0.3 or less, it is considered of clinical significance and a Go decision to phase 3 will be likely.

If the difference is between -0.3 and -0.1, a decision will be made based on other data, e.g., efficacy in secondary endpoints and safety data.

The sample size is determined based on the probability of making a correct decision given the true effect size (i.e., efficacy scenario). Assuming the standard deviation is 0.7 unit, Table 1 below presents the summary of probabilities for observing the efficacy.

Table 1. Probability of making a Go, Pending, or No-Go decision, given various true effect size in $\Delta\Delta\text{ICSS}$.

True $\Delta\Delta\text{ICSS}$	Observed $\Delta\Delta\text{ICSS} \leq -0.3$ (Go Decision)	Observed $\Delta\Delta\text{ICSS}$ between -0.3 and -0.1 (Pending Decision)	Observed $\Delta\Delta\text{ICSS} > -0.1$ (No-Go Decision)
0.0	3.0%	23.3%	73.8%
0.1	9.9%	40.1%	50.0%
0.2	26.2%	48.6%	25.2%
0.3	50.0%	40.2%	9.8%
0.4	74.8%	22.7%	2.6%

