9.2 Determination of Sample Size

This study is expected to enroll 50 subjects in each treatment group so a total of 100 subjects will be randomized. Assuming a 20% drop out rate, 40 subjects per group are expected to complete the study.

According to the results from the US Phase II study, assuming the standard deviation is 0.7 unit for the change from baseline in the pre- to post-CAE[®] inferior corneal fluorescein staining (ICSS) score and the mean of the change from baseline in the pre- to post-CAE ICSS score is about 0.65, the efficacy results will be very promising if the difference in the mean of ICSS change for the placebo and treatment groups are greater than 0.3. If the difference < 0.1, the efficacy may not be promising.

If 40 subjects in each group will complete the study, the probability for observing the efficacy < 0.1 in this study will be about 74% if the study drug is not effective in the treatment group. If the difference in the efficacy between the treatment and placebo groups is >0.4, the probability for observing the efficacy > 0.3 in this study will be at least 75%. Other possibilities are summarized in the table below.

ICSS Actual Mean Difference	Ideal Region Mean difference ≥ 0.3	Consideration Region Mean Difference [0.1, 0.3)	Unsatisfactory Region Mean difference < 0.1
0.0	3.0%	23.3%	73.8%
0.1	9.9%	40.1%	50.0%
0.2	26.2%	48.6%	25.2%
0.3	50.0%	40.2%	9.8%
0.4	74.8%	22.7%	2.6%

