9.5 Efficacy and Safety Analysis

9.5.1 Efficacy Analysis

9.5.1.1 Primary Efficacy Analyses

For primary efficacy endpoints, the pre- to post-CAE ICSS change will be calculated as post-CAE ICSS score-pre-CAE ICSS score. The change from baseline will be calculated as visit (post-CAE-pre-CAE)-baseline (post-CAE-pre-CAE) such that a positive difference indicates the change at study visit is larger than that at baseline. In addition, treatment comparisons between treatment and placebo groups will be calculated as treatment – placebo, such that a negative result indicates a better score for the treatment group (i.e., the treatment group have a smaller increase in dry eye signs or symptoms than the placebo group).

ANCOVA models will be used to compare the change from baseline in the pre- to post-CAE[®] inferior corneal fluorescein staining at Day 57 (Visit 6) (measured by the Ora Calibra[®] scale), between 0.25% HBM9036 Ophthalmic Solution and Placebo. The ANCOVA models will include the change in pre- to post-CAE ICSS at baseline as a covariate. The primary analysis will use LOCF imputation to have a full accounting of the FAS at the Day 57 visit, as described in Section 9.7.

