6.2.1 Definition

For the primary efficacy endpoint, the pre- to post-CAE[®] ICSS change will be calculated as post-CAE[®] ICSS– pre-CAE[®] ICSS, noted as Δ ICSS. The change from baseline in Δ ICSS will be calculated as visit (Δ ICSS) – baseline (Δ ICSS) (denoted as $\Delta\Delta$ ICSS). Treatment comparisons between treatment and placebo groups will be calculated as treatment – placebo (denoted as $\Delta\Delta\Delta$ ICSS). A negative value indicates a better outcome for the treatment group (i.e., the treatment group increase more or worsen less in dry eye signs or symptoms than the placebo group).

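### Do the unsigned true effects in SAP Table 1 make its Go/No-Go probabilities wrong?

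*SAP*

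**What the plan says.** SAP 1.4 states the Phase 3 decision rule for the HBM9036-minus-placebo difference in the primary endpoint: "if the difference is -0.3 or less, it is considered of clinical significance and a Go decision to phase 3 will be likely". Differences above -0.1 are treated as of little clinical relevance, and values between the two cut-offs are left to a decision on other data. The column heads of Table 1, captioned "Probability of making a Go, Pending, or No-Go decision, given various true effect size in" ΔΔICSS, carry the same negative cut-offs. The first column, the true effect, reads 0.0, 0.1, 0.2, 0.3, 0.4.

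The direction of the contrast is defined twice. SAP 6.2.1 takes treatment minus placebo and says "A negative value indicates a better outcome for the treatment group". Protocol 9.5.1.1 uses the same subtraction, "such that a negative result indicates a better score for the treatment group".

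Protocol 9.2 has a table with the same row values and the same 15 probabilities, but on a positive-benefit scale: results are "very promising if the difference in the mean of ICSS change for the placebo and treatment groups are greater than 0.3", and its regions are cut at 0.3 and 0.1 with no minus sign.

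Two smaller points of wording belong here. SAP 6.2.1 explains a negative value as meaning that "the treatment group increase more or worsen less in dry eye signs or symptoms than the placebo group". It also names the between-group difference ΔΔΔICSS, whereas Table 1 heads its columns ΔΔICSS.

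**The concern.** The true and observed columns of Table 1 carry the same symbol, so a reader is entitled to assume one scale. On that assumption the four non-zero rows describe a drug that is worse than placebo, yet they show a Go probability that climbs as the harm grows. Table 1 is where the SAP shows the operating characteristics behind the sample size and the Phase 3 decision. If the probabilities themselves were wrong, the justification for 50 randomised per arm would fall, and so would the stated chance of a correct decision.

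The gloss in SAP 6.2.1 adds to the unease. Taken alone, its first verb suggests that a negative value means more growth in signs and symptoms, the reverse of the protocol.

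**Working it through.** **Inputs.** SD from SAP 1.4: "Assuming the standard deviation is 0.7 unit, Table 1 below presents the summary of probabilities for observing the efficacy". Evaluable subjects per arm, also SAP 1.4: "Assuming a 20% drop out rate, 40 subjects per group are expected to complete the study". Allocation is 1:1 (SAP 1.5). Cut-offs are -0.3 and -0.1 (SAP 1.4).

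**Formulas.** Take the observed difference as normal around the true difference d, with

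SE = 0.7 × √(2/40) = 0.1565.

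- P(Go) = Φ((-0.3 - d)/SE)
- P(No-Go) = 1 - Φ((-0.1 - d)/SE)
- P(Pending) = 1 - P(Go) - P(No-Go)

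**Step 1: reproduce the printed table with negative true effects.** For d = -0.4, P(Go) = Φ(0.1/0.1565) = Φ(0.639) = 73.9%. The full table, as Go / Pending / No-Go in %:

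| True difference | Computed | Printed |
|---|---|---|
| 0.0 | 2.8 / 23.4 / 73.9 | 3.0 / 23.3 / 73.8 |
| -0.1 | 10.1 / 39.9 / 50.0 | 9.9 / 40.1 / 50.0 |
| -0.2 | 26.1 / 47.7 / 26.1 | 26.2 / 48.6 / 25.2 |
| -0.3 | 50.0 / 39.9 / 10.1 | 50.0 / 40.2 / 9.8 |
| -0.4 | 73.9 / 23.4 / 2.8 | 74.8 / 22.7 / 2.6 |

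All 15 cells agree within 0.95 points. The largest gaps are No-Go at -0.2 (26.145 against 25.2) and Go at -0.4 (73.855 against 74.8). An exact calculation gives equal Go and No-Go probabilities at -0.2, while the printed pair is 26.2 and 25.2. Simulation would produce a gap of that kind, but the documents do not state the method.

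**Step 2: the same formulas with the labels as printed.** For d = +0.4, P(Go) = Φ(-0.7/0.1565) = Φ(-4.47), about 0.0004%.

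| True difference | Computed | Printed |
|---|---|---|
| +0.1 | 0.53 / 9.5 / 89.9 | 9.9 / 40.1 / 50.0 |
| +0.2 | 0.07 / 2.7 / 97.2 | 26.2 / 48.6 / 25.2 |
| +0.3 | 0.006 / 0.5 / 99.5 | 50.0 / 40.2 / 9.8 |
| +0.4 | 0.0004 / 0.07 / 99.9 | 74.8 / 22.7 / 2.6 |

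None of these 12 cells matches; the gaps run from about 9 to 97 points. The error is therefore in the sign of the row labels and not in the probabilities.

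**Step 3: check that 40 per arm is the basis.** With 50 per arm, SE = 0.7 × √(2/50) = 0.14. Go at -0.1 is then 7.7% (printed 9.9%) and Pending at -0.2 is 52.5% (printed 48.6%). The table rests on 40 completers per arm, as the text says, and 40/(1 - 0.2) = 50 gives the number randomised.

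**Step 4: find the source.** Changing the sign of both rows and cut-offs leaves every probability unchanged. The protocol table, positive throughout, is therefore the same table as the SAP's with negative rows. The SAP carried over the protocol's row labels and probabilities and changed the sign of the cut-offs only.

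**The case for a change.** The strongest case for a correction is that this is a definite, reproducible inconsistency inside a decision table, in a document to be signed before unblinding, and that repair would cost four minus signs. Nothing in the SAP says the rows are magnitudes of benefit. Loss of the signs in PDF conversion is unlikely, because minus signs survive in the column heads of the same table. All of that stands.

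What does not stand is the suggestion that a reader could be misled, or would need the protocol to recover the meaning. The sentences just above the table say that more negative is better. The caption speaks of effect size, which is often given as a magnitude. A Go probability that rises down the rows can only describe growing benefit.

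The two added points are weaker. SAP 6.2.2 itself speaks of between-group differences in ΔΔICSS, so the caption of Table 1 follows the SAP's own usage and only the column heads are loose shorthand. In the gloss in SAP 6.2.1, one verb is badly chosen, but it sits beside a clause calling the outcome better and another saying worsening is less. Both agree with Protocol 9.5.1.1, and the subtraction that is programmed is unambiguous.

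**Conclusion.** A clerical slip with no consequence for the trial. The true-effect labels 0.1 to 0.4 in SAP Table 1 lack minus signs. The printed probabilities are right, to within 0.95 points, for true differences of 0.0, -0.1, -0.2, -0.3 and -0.4. The 9 to 97 point gaps in Step 2 belong to a literal reading that no one applying the rule would adopt.

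The number randomised, the cut-offs, the correctly signed rule in the text and the primary ANCOVA are all untouched. The rule will be applied to the observed treatment-minus-placebo difference, and that step does not use the row labels of Table 1.

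The conclusion rests on a normal approximation with the plan's own SD of 0.7 and 40 completers per arm. A t distribution with 78 degrees of freedom gives almost the same values, for example 2.95 / 23.29 / 73.76% at a true difference of zero. The labels could be tidied if the SAP were reopened for another reason, but this point alone does not call for a change.
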